9.8.2 Collection and Reporting of SAEs

When an SAE occurs through the AE collection period, it should be reported according to the following procedure:

An SAE form must be completed in English and signed by the Investigator immediately or within 24 hours of the first onset or notification of the event. The information should be completed as fully as possible but contain, at a minimum:

- A short description of the event and the reason why the event is categorized as serious
- Subject identification number
- Investigator's name
- Name of the study medication(s)
- Causality assessment

The SAE form should be transmitted within 24 hours to the attention of the contact listed in **Section 1.0**.

Any SAE spontaneously reported to the Investigator following the AE collection period should be reported to the sponsor if considered related to study participation.

Reporting of Serious PTEs will follow the procedure described for SAEs.

9.8.3 Reporting of Abnormal LFT

If a subject is noted to have ALT or AST elevated $>3 \times \text{ULN}$ on 2 consecutive occasions, the abnormality should be recorded as an AE. In addition, an LFT Increases eCRF must be completed by providing additional information on relevant recent history, risk factors, clinical signs and symptoms, and results of any additional diagnostic tests performed.

If a subject is noted to have ALT or AST $>3 \times \text{ULN}$ and total bilirubin $>2 \times \text{ULN}$ for which an alternative etiology has not been identified, the event should be recorded as an SAE and reported as per **Section 9.8.2**. The Investigator must contact the Medical Monitor for discussion of the relevant subject details and possible alternative etiologies, such as acute viral hepatitis A or B or other acute liver disease or medical history/concurrent medical conditions. Follow-up laboratory tests as described in **Section 9.1.8** must also be performed. In addition, an LFT Increases eCRF must be completed and transmitted with the SAE form (as per **Section 9.8.3**).

9.9 Follow-up of SAEs

If information is not available at the time of the first report becomes available at a later date, the Investigator should complete a follow-up SAE form or provide other written documentation and fax it immediately within 24 hours of receipt. Copies of any relevant data from the hospital notes (e.g., ECGs, laboratory tests, discharge summary, postmortem results) should be sent to the addressee if requested.

All SAEs should be followed up until resuspension or the permanent outcome of the event. The timelines and procedures for follow-up reports are the same as those for the initial report.

9.9.1 Safety Reporting to Investigators, IRBs or IECs, and Regulatory Authorities

The sponsor will be responsible for reporting all suspected unexpected serious adverse reactions (SUSARs) and any other applicable SAEs to regulatory authorities and IRBs or IECs, as applicable, in accordance with national regulations in the countries where the study is conducted. Relative to the first awareness of the event by/or further provision to the sponsor or sponsor's designee, SUSARs will be submitted to the regulatory authorities as an expedited report within 7 days for fatal and life-threatening events and 15 days for other serious events, unless otherwise required by national regulations. The sponsor will also prepare an expedited report for other safety issues that might materially alter the current benefit-risk assessment of an investigational medicinal product or that would be sufficient to consider changes in the investigational medicinal products administration or in the overall conduct of the trial. The investigational site also will forward a copy of all expedited reports to his or her IRB or IEC in accordance with national regulations.

10.0 STUDY-SPECIFIC COMMITTEES

The Safety Review Group (SRG) will be comprised of the Investigator, Medical Monitor, Cerevance Medical Officer and may include other sponsor representatives. A pharmacokineticist and other subject matter experts may participate as needed. The responsibilities of the SRG are outlined in **Section 6.1.3**.

11.0 DATA HANDLING AND RECORDKEEPING

AEs, PTEs, medical history, and concurrent conditions will be coded using the Medical Dictionary for Regulatory Activities (MedDRA). Drugs will be coded using the World Health Organization (WHO) Drug Dictionary. All terms will be coded using the dictionary version available at the start of the study.

11.1 CRFs (Electronic)

Completed eCRFs are required for each subject who signs an informed consent.

The sponsor or its designee will supply investigative sites with access to eCRFs. The sponsor will make arrangements to train appropriate site staff in the use of the eCRF. These forms are used to transmit the information collected in the performance of this study to the sponsor and regulatory authorities. eCRFs must be completed in English. Data are transcribed directly onto eCRFs.

After completion of the entry process, computer logic checks will be run to identify items, such as inconsistent dates, missing data, and questionable values. Queries may be issued by sponsor personnel (or designees) and will be answered by the site.

Corrections to eCRFs are recorded in an audit trail that captures the old information, the new information, identification of the person making the correction, the date the correction was made, and the reason for the change. Reasons for significant corrections should additionally be included.

The Investigator must review the eCRFs for completeness and accuracy and must sign and date the appropriate eCRFs as indicated. Furthermore, the Investigator must retain full responsibility for the accuracy and authenticity of all data entered on the eCRFs.

eCRFs will be reviewed for completeness and acceptability at the study site during periodic visits by study monitors. The sponsor or its designee will be permitted to review the subject's medical and hospital records pertinent to the study to ensure the accuracy of the eCRFs. The completed eCRFs are the sole property of the sponsor and should not be made available in any form to third parties, except for authorized representatives of appropriate governmental health or regulatory authorities, without the written permission of the sponsor.

11.2 Record Retention

The Investigator agrees to keep the records stipulated in **Section 11.2** and those documents that include (but are not limited to) the study-specific documents, the identification log of all participating subjects, medical records, temporary media such as thermal sensitive paper, source worksheets, all original signed and dated ICFs, subject authorization forms regarding the use of personal health information (if separate from the ICFs), an electronic copy of eCRFs, including the audit trail, and detailed records of drug disposition to enable evaluations or audits from regulatory authorities, the sponsor or its designees. Any source documentation printed on degradable thermal sensitive paper should be photocopied by the site and filed with the original in the subject's chart to ensure long-term legibility. Furthermore, ICH E6 Section 4.9.5 requires the Investigator to retain essential documents specified in ICH E6 (Section 8) until at least 2 years after the last approval of a marketing application for a specified drug indication being investigated or, if an application is not approved, until at least 2 years after the investigation is discontinued and regulatory authorities are notified. In addition, ICH E6 Section 4.9.5 states that the study records should be retained until an amount of time specified by applicable regulatory requirements or for a time specified in the Clinical Study Site Agreement between the Investigator and sponsor.

Refer to the Phase 1 Site Specifications document for the sponsor's requirements on record retention. The Investigator should contact and receive written approval from the sponsor before disposing of such documents.

12.0 STATISTICAL METHODS

12.1 Statistical and Analytical Plans

A statistical analysis plan (SAP) will be prepared and finalized prior to unblinding of the subject's treatment assignment. This document will provide further details regarding the definition of analysis variables and analysis methodology to address all study objectives.

A targeted data review will be conducted prior to unblinding of the subject's treatment assignment. This review will assess the accuracy and completeness of the study database, subject evaluability, and appropriateness of the planned statistical methods.

12.1.1 Analysis Sets

Safety Set

The Safety Analysis Set will consist of all subjects who are enrolled and receive study drug. Subjects in this analysis set will be used for demographic, baseline characteristics, and safety summaries.

PK Set

The PK set will consist of all subjects who receive study drug and have at least 1 measurable plasma concentration.

If any subjects are found to be non-compliant in dosing schedule or with incomplete data, a decision will be made on a case-by-case basis as to their inclusion in the analysis but will be presented in the subject listings.

12.1.2 Analysis of Demographics and Other Baseline Characteristics

Descriptive statistics (N, mean, SD, median, minimum, and maximum) will be generated for continuous demographic variables and baseline characteristics variables (age, height, weight, and BMI) for pooled placebo, CVN766 dose level, CVN766 overall, and overall. The number and percentage of subjects in each class of the categorical demographic variables and baseline characteristics variables (gender, ethnicity, and race) will be tabulated for pooled placebo, each CVN766 dose level, CVN766 overall, and overall. Individual subject demographic and baseline characteristics data will be listed.

Demographic variables of screen failure subjects and reasons for screen failures will be summarized overall for subjects who are screened but not enrolled in the study. Individual demographic characteristics, date of informed consent, and reason for screen failure will be listed.

12.1.3 PK Analysis

The concentration of CVN766 in plasma and CSF will be summarized by dose over each scheduled sampling time using descriptive statistics. Individual concentration data versus time will be presented in a data listing. Individual and mean plasma and CSF concentration data will be presented graphically. Descriptive statistics (arithmetic mean, SD, median, minimum and maximum) will be used to summarize the plasma and CSF PK parameters for CVN766. In addition, geometric mean and coefficient of variation will be computed.

The effect of fed/fasting state on PK and bioavailability of CVN766 will be characterized.

Plots of C_{max} and AUCs, as well as dose-normalized C_{max} and AUCs, versus doses, will be generated.

Dose proportionality will be tested for CVN766 C_{max} and AUCs using a power model.

A more detailed analysis will be presented in the SAP.

12.1.4 Safety Analysis

12.1.4.1 AEs

All AEs will be coded by system organ class (SOC) and preferred term (PT) using MedDRA. Treatment-emergent AEs with onset occurring within 30 days (onset date – last date of dose +1 \leq 30) after study drug administration will be listed and included in the summary tables. Treatment-emergent AEs will be summarized by pooled placebo, each CVN766 dose level and CVN766 overall by SOC and PT. The following summary tables will be included in the report: summary of TEAEs and drug-related AEs, relationship of AEs to study drug (related vs. not-related), severity of AEs, and related AEs. AEs leading to study drug discontinuation and SAEs will be listed. Data listings will be provided for all AEs, including PTE, TEAEs, AEs leading to study drug discontinuation, and SAEs. All AEs will be listed.

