
clinical laboratory results from a minimum of 5 subjects in the current cohort),
 
 2. Escalate to the next planned cohort or alternative dose levels (e.g., lower, intermediate, or higher) in multiple-dose cohorts (based on a review of available data, including at least 48 hours post 7th dose safety data from a minimum of 5 subjects in the current cohort), 3. Add additional dose cohort(s) in either the single- or multiple-dose studies, 4. Increase the duration of dosing in the multiple-dose cohorts from 7 days to ≤ 14 days, 
In addition, if 2 or more subjects in a single cohort experience the same type of serious or medically significant event, further dosing will be withheld until the SRG investigates the events. Based on this assessment, the SRG will determine if the study should be terminated or continued and whether modification of planned dose levels and/or implementation of additional safety monitoring is indicated.
	

Primary Objective:
 
To characterize the safety and tolerability profile of escalating dose levels of CVN766 suspension when administered as a single oral dose or daily oral doses for 7 days in healthy subjects and determine the recommended phase 2 dose (RP2D).
	

Secondary Objectives:
 
 • To characterize the single-dose PK profile of CVN766 in plasma and CSF • To characterize the multiple-dose PK profile of CVN766 in plasma and CSF • To assess the effect of food on the bioavailability of CVN766 	

Exploratory Objectives:
 
 • To explore possible drug metabolic enzyme and transporter polymorphisms that may contribute to variability in CVN766 PK, pharmacodynamics, or safety 	

Subject Population: Healthy male and female subjects 18 to 55 years old
	

Number of Subjects:
 
Each dose cohort: 8 subjects (6 active:2 placebo) Estimated total: 64 subjects (5 single-dose cohorts, 3 multiple-dose cohorts)
	
Number of Sites:
 
2 (Australia)

Dose Level(s):
 
Planned single-dose levels are placebo, 5 mg, 15 mg, 45 mg, 125 mg, and 250 mg CVN766. Planned multiple dose levels are placebo, 45 mg, 125 mg, and 250 mg CVN766.
	
Route of Administration:
 
Oral

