The sampling of whole blood for pharmacogenomic and genotyping analysis is mandatory; eligible subjects sign the ICF, which outlines the retention of pharmacogenomic and genotyping analysis in order to participate in this study. DNA samples will be collected and may be used to evaluate drug metabolic enzyme and transporter polymorphisms that may contribute to the variability in the PK of CVN766. Also, since pharmacogenomics is an evolving science, many genes and their functions are not yet fully understood. Future data may suggest a role of some of these genes in drug response, which may lead to additional hypothesis-generating exploratory research and diagnostic development on stored samples.

- Endpoints:

The primary endpoints of this study will be the following: percentage of subjects who experience at least one treatment-emergent adverse event (TEAE); percentage of subjects with abnormal and CS safety laboratory, vital signs, or ECG test results at least once post-dose.

The secondary endpoints will be the following plasma PK parameters of CVN766: C_{max} , AUC_{24} , AUC_{∞} , $t_{1/2z}$, AUC from time 0 to end of the dosing interval, accumulation ratio, time to steady-state, steady-state C_{max} , and steady-state C_{min} .

The additional endpoints may include the following plasma PK parameters of CVN766: t_{max} , CL/F, V_z/F , CL/F_{ss}, V_z/F_{ss} , and plasma: CSF ratio.

Exploratory endpoints may include characterization of metabolic enzyme and transporter polymorphisms and/or

Statistical Considerations:

Safety:

AEs will be presented in listings, and TEAEs will be summarized. Individual results of laboratory tests (hematology, chemistry, and urinalysis) will be recorded at baseline and post-dose, and changes from baseline will be summarized using shift tables. Individual vital signs will be recorded, and observed values and changes from baseline will be summarized. Individual results of quantitative ECG parameters from the 12-lead safety ECGs will be listed, and observed values and changes from baseline will be summarized. All summaries will be performed by placebo, each CVN766 dose level (fasted and fed separately), and CVN766 single-dose overall, and separately CVN766 multiple-dose cohorts overall. Placebo data will be pooled across single-dose cohorts and separately pooled across multiple-dose cohorts. Physical exam findings will be presented in data listings.

PK Measures:

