12.1.4.2 Clinical Laboratory Evaluation

Individual results of laboratory tests from hematology, chemistry, and urinalysis that are abnormal and CS will be summarized and listed. Baseline, post-dose, and change from baseline to post-dose laboratory data will be summarized for pooled placebo, each CVN766 dose level, and CVN766 overall. All clinical laboratory data will be listed.

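### Section 12 and the synopsis give contradictory groupings for the safety tables; read literally, Section 12 mixes single-dose and 7-day subjects at 45, 125 and 250 mg

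*Protocol*

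**What the plan says.** The two texts describe the same safety tables differently.

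- **Section 12.1.4.1 (AEs):** "Treatment-emergent AEs will be summarized by pooled placebo, each CVN766 dose level and CVN766 overall by SOC and PT". There is one placebo column and one active total, with no mention of study part or of fed and fasted periods.
- **Section 12.1.4.2 (laboratory):** baseline, post-dose and change data "will be summarized for pooled placebo, each CVN766 dose level, and CVN766 overall". Sections 12.1.4.3 (vital signs) and 12.1.4.4 (ECGs) name the same groups.
- **Synopsis, Statistical Considerations, Safety:** all summaries are by placebo, "each CVN766 dose level (fasted and fed separately), and CVN766 single-dose overall, and separately CVN766 multiple-dose cohorts overall". It adds: "Placebo data will be pooled across single-dose cohorts and separately pooled across multiple-dose cohorts".

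The protocol file holds two versions, and the conflict stands in both. Optional Cohort S3a (45 mg, fasted only) appears only in the amended one. Section 12.1 leaves further analysis detail to an SAP that must be final before unblinding. It does not say which of the two groupings governs.

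**The concern.** The TEAE percentage is a primary endpoint (Section 5.2.1) and counts subjects with at least one event. Such a percentage can be expected to rise with the number of doses, the days observed and the procedures undergone. The two lowest doses are given only as single doses, while the three higher doses are given both once and daily for 7 days. If one row per dose merges both regimens, dose is confounded with regimen between 15 mg and 45 mg, and no dose row has a placebo group with the same regimen mix. In the synopsis, the primary objective includes determining a recommended phase 2 dose, so a reader is likely to look down the dose rows for a gradient.

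**Working it through.** **Inputs from the protocol.** For the single-dose part, the synopsis says: "Planned single-dose levels are placebo, 5 mg, 15 mg, 45 mg, 125 mg, and 250 mg CVN766". The 7-day part uses only the three highest of these doses. Allocation is 6 active to 2 placebo in each cohort of 8. AEs are routinely collected until 14 days after the last dose (Section 9.8.1.1): about 14 days after a single dose and about 21 days in a 7-day cohort, a ratio of about 1.5. Section 12.1.4.1 would count onsets up to 30 days, but routine collection stops at 14, so the shorter period governs what is observed.

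**The plan's own figure.** "Estimated total: 64 subjects (5 single-dose cohorts, 3 multiple-dose cohorts". 5 × 8 + 3 × 8 = 40 + 24 = 64, which reproduces.

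**Composition under a literal Section 12 table.**

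| Column | Single-dose part | 7-day part | 7-day share |
|---|---|---|---|
| 5 mg, 15 mg (each) | 6 | 0 | 0% |
| 45 mg | 6 | 6 | 50% (6/18 = 33.3% with S3a) |
| 125 mg, 250 mg (each) | 6 | 6 | 50% |
| Pooled placebo | 10 | 6 | 37.5% |
| CVN766 overall | 30 | 18 | 37.5% |

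**Expected percentages with no dose effect.** Let p1 be the TEAE risk of a subject in the single-dose part and p7 that of a 7-day subject. Both are assumptions, because the protocol states no rates.

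- 5 and 15 mg: p1
- 45, 125 and 250 mg: (6·p1 + 6·p7)/12
- Artificial step: (p7 − p1)/2
- Pooled placebo: (10·p1 + 6·p7)/16

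*(a) Risk follows only the collection period.* p7 = 1 − (1 − p1)^1.5.

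| p1 | p7 | Higher-dose rows | Step (points) | Pooled placebo |
|---|---|---|---|---|
| 20% | 28.4% | 24.2% | 4.2 | 23.2% |
| 30% | 41.4% | 35.7% | 5.7 | 34.3% |
| 40% | 53.5% | 46.8% | 6.8 | 45.1% |
| 50% | 64.6% | 57.3% | 7.3 | 55.5% |

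*(b) Risk doubles, 30% to 60%.* Higher-dose rows are (6 × 0.30 + 6 × 0.60)/12 = 45%, a step of 15 points. Pooled placebo is (10 × 0.30 + 6 × 0.60)/16 = 41.25%, so 5 and 15 mg sit 11.25 points below placebo and the higher doses 3.75 above.

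*(c) Equal independent risk at each dose.* p7 = 1 − (1 − p1)^7. For p1 from 10% to 30% the step is 21 to 31 points. This is an upper extreme.

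**The 45 mg row.** The formula gives S3 subjects the same risk as other single-dose subjects, so it applies cleanly only at 125 and 250 mg. S3 subjects are dosed twice, at least 14 days apart, and followed for 14 days after the second dose: at least 14 + 14 = 28 days, longer than the 7-day cohorts. They also have a lumbar puncture in the fasted period. Section 12 does not separate the two periods, so this would push the 45 mg row up. S3a would pull it down: with 12 single-dose and 6 seven-day subjects, the regimen step there is (p7 − p1)/3.

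**Active overall against pooled placebo.** The 7-day share is 18/48 = 6/16 = 37.5% in both, because allocation is 3:1 throughout. With S3a it is 18/54 = 6/18 = 33.3% in both. This contrast is not distorted.

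**After splitting by part.** With no dose effect, every single-dose row and its placebo have expectation p1 and every 7-day row and its placebo p7 (S3 again treated like the other single-dose cohorts). The artificial step is zero.

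**The case against.** Much can be said against a stronger reading, and most of it stands.

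- A reader might infer that Section 12 orders the two regimens to be merged at 45, 125 and 250 mg and that the synopsis orders them split. Neither text says so. Both refer to the dose levels in the same words. Section 12 is silent on part, and in the synopsis the split of the dose rows is only implied by the part-specific placebo and totals. Merging is the literal reading of Section 12, not a stated rule.
- A reader might infer that all four primary endpoints are affected. For clinically significant laboratory, vital-sign and ECG abnormalities, Section 12 says only that they are summarized and listed. Its grouping attaches to baseline, post-dose and change data, where the changes are additional endpoints (Section 5.2.3). Only the TEAE percentage is a primary endpoint grouped this way.
- A reader might infer a large false dose trend. That requires assumed risk ratios well above the ratio of collection periods. The artefact is one step, and the 125 and 250 mg rows stay level with each other.
- Lumbar puncture and longer follow-up are not peculiar to the 7-day part, since S3 has both.
- The safety analysis is descriptive, escalation rests on cohort-by-cohort blinded review, and all AEs are listed, so the data can be re-tabulated by part.
- Table layout commonly belongs to the SAP, which is not shown and may settle it.

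None of this reconciles the placebo, overall and fed/fasted columns. On those the protocol gives two incompatible instructions, and an SAP author could cite either.

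**Conclusion.** The contradiction is established from the text alone and needs no assumption. The possible artefact is conditional: it requires that Section 12 be applied literally and that per-subject TEAE risk be higher in the 7-day cohorts. Its size, about 4 to 7 points, assumes that risk follows only the collection period and lies between 20% and 50% in the single-dose part. Larger values rest on risk ratios the protocol neither gives nor supports. The documents do not support a claim that the safety conclusions as a whole would be biased. This is a modest defect in one primary safety table, worth correcting because the sponsor's own synopsis already contains the better rule.

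**What to change.** In Sections 12.1.4.1 to 12.1.4.4, replace the single placebo pool and single active total with the synopsis grouping. State explicitly what the synopsis only implies for the dose rows: dose levels, placebo and CVN766 overall are each presented within the single-dose part and within the multiple-dose part, with 45 mg fasted and fed shown separately. The SAP should follow the same layout and be final before unblinding, as Section 12.1 already requires. No change to design, data collection or sample size is needed. The cost is wording and more table columns with smaller counts: 6 per active row (12 for single-dose 45 mg fasted if S3a is shown with S3), and placebo groups of 10 and 6 instead of 16.
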